The stimulation patterns and pulse patterns will be selected by the neurosurgeon to deliver stimulation therapy to the chosen electrode contact configurations (refer to Supplemental Materials Appendix C on stimulation contact configurations) estimated to provide selective dorsal column activation.

Approximately 10-20 electrode contact Groups will be performed during the study. Paresthesia maps will be created according to the region in which the neuromonitoring reports EMG activation.

Initially a central electrode bi-pole or tri-pole will be used, and the stimulus amplitude will be increased until neuromonitoring is used to identify an activation threshold (frequency will be fixed). At that time, 10-20 predefined stimulation electrode Groups will be stimulated (see Supplemental Material Appendix C for exemplar electrode patterns) at an amplitude below threshold. The various electrode Groups will be created using the Study Electrode in low-resolution and high-resolution configurations. Low-density electrode configurations will use 2 or more electrodes as a grouped-contact while high-resolution will use only one electrode. After the first group of stimulation contacts is activated, the EMG patterns will be recorded. Group 1 of stimulation contacts will be de-activated. A Group 2 of stimulation contacts will be activated, followed by recording the EMG responses. It may be necessary to alternate and re-activate Group 1 to verify repeatability. Group 3-Group 20 will be sequentially performed. This study procedure will be allowed for approximately 20 minutes, which should be

sufficient to collect the necessary data of high-resolution electrode contact patterns. A designated team member will record the EMG results (see case report form, Appendix A). Once the study data is collected, the Study Electrode will be removed from the subject.

< End of Study >

Step 4-b. Stimulation with Standard Electrode (Standard Procedure)

The procedure will continue as standard of practice. The Permanent Electrode will be placed and tested (Step 4) using the standard of care lateralization using Neuromonitoring. Once the location is confirmed, the Permanent Electrode may then be secured using sterile Nurolon suture per standard of care.

Step 5. Tunneling, Implant of the battery, and surgical closure (Standard Procedure)

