- iii. The proposed study will identify a paresthesia stimulation threshold, and then perform mapping between the dermatome where EMG-based Neuromonitoring demonstrates activation. Multiple Study Electrode contact Groups will be stimulated and recorded as to where the EMG recruitment is generated. The Groups will be designed to demonstrate selective stimulation, low-back stimulation, and bilateral paresthesia coverage. According to standard procedure, the Permanent Electrode is activated using multiple stimulation groups. Stimulation groups for the Study Electrode will be chosen such that at least two electrode Groups will be identical to those used for the Permanent Electrode. Additionally, the Study Electrode will be configured using low-density and high-resolution patterns as a direct comparison. The selectivity of paresthesia will be characterized for these Study Electrode configurations. The data will be analyzed to determine trends across subjects in whether the high-resolution stimulation improves the targeting of therapy to a focal number of dermatomes.

- iv. The study hypothesis is that the high-resolution Study Electrode will generate paresthesia that is focused to a more selective (smaller) dermatomal region than the currently available paddle electrodes according to the paresthesia maps. We further hypothesize that the Study Electrode will provide dorsal root activation and bi-lateral activation. We finally hypothesize that the Study Electrode may selectively provide paresthesia to the lower-back dermatomes. We do not believe that the Permanent Electrode will be able to achieve these outcomes.
- v. The study is designed to perform a relative comparison between high-resolution and low-density Electrode Groups using the Study Electrode. Repetitive stimulation contact Groups may be used (as defined in the protocol) to ensure repeatability of EMG responses. Statistical analysis of Study Electrode contact Groups will be explored but may not be statically significant as the exact surgical position of the electrodes will be different for each subject. The analyses will be compared between the stimulation amplitudes between the high and low-density Groups.
- vi. We will compute a dermatomal heat-map describing the stimulation dermatome observed by EMG. The 10-20 Groups of stimulation will allow us to answer the specific research questions:

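### The Group 1 repeat is optional and D.v cites a repeat rule that the protocol text does not define, so the required measurements give no estimate of within-session change

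*Combined protocol and SAP*

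**What the plan says.** Section B, Step 4-a describes the session in sequence. A threshold is sought at the start: "Initially a central electrode bi-pole or tri-pole will be used". Then "10-20 predefined stimulation electrode Groups will be stimulated" "at an amplitude below threshold". Group 1 is activated, recorded and switched off, and Group 2 follows. Next comes the only sentence on repeats in the step: "It may be necessary to alternate and re-activate Group 1 to verify repeatability". After that, "Group 3-Group 20 will be sequentially performed". On time, the step says: "This study procedure will be allowed for approximately 20 minutes".

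Section D, item v names the comparison of high-resolution with low-density Groups on the Study Electrode as what the study is designed for, and includes stimulation amplitude among the things compared. On repeats it says: "Repetitive stimulation contact Groups may be used (as defined in the protocol) to ensure repeatability of EMG responses".

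The supplied text contains no other rule on repeats. It states no randomised or alternating order of Groups, and no time or order term in the analysis.

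**The concern.** Item v expects repeats to secure repeatability and points to the protocol for their definition. Step 4-a only allows a repeat. It gives no trigger, count, timing or criterion for agreement. A team can follow the plan exactly and repeat nothing in any subject.

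Research question (2) in Section D asks whether selectivity differs between low- and high-resolution configurations. To read such a difference, one needs to know how far the same Group, at the same settings, changes between the start and the end of the session. Without that, a difference between an early and a late Group could reflect configuration, elapsed time or both. Once the Study Electrode has been removed, the information cannot be recovered.

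**Working it through.** The plan gives no sample size, variance or drift figure, so there is nothing of its own to reproduce. The check is whether the required measurements can identify drift at all.

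**Inputs from the documents**
- Groups: 10 to 20, run sequentially (Step 4-a).
- Session: about 20 minutes (Step 4-a).
- Amplitude step: 0.2 mA (Section B, Study Pulse Generator System).
- Subjects: 10 (Section A) or 20 (Sections B and C). Both are carried through.

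**Assumptions, not in the documents**
- Drift is linear, with total size D over the session. D = 0.2 to 2.0 mA is used for illustration.
- Sigma is the SD of a single reading. Results are given in multiples of it.

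**1. Pace.** 20 min / 20 Groups = 1 min and 20 min / 10 Groups = 2 min. One extra run takes 1/20 = 5% to 2/20 = 10% of the session.

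**2. Each Group once, fixed order.** The model has one effect per Group plus one drift term.
- 10 Groups: 11 parameters, design-matrix rank 10.
- 20 Groups: 21 parameters, rank 20.
- Pooling subjects run in the same order (subject intercepts, 19 Group contrasts, one drift term; 20 Groups): rank 29 of 30 for 10 subjects and 39 of 40 for 20.

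The rank is one short each time, so drift and Group effects are aliased.

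**3. One repeat of Group 1.** The drift estimate is the repeat minus the first reading, divided by the fraction f of the session between them. SE = √2 × sigma / f.

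| Position of repeat | f | SE of full-session drift |
|---|---|---|
| After Group 2, 10 Groups (11 runs) | 2/10 | 1.414/0.2 = 7.1 sigma |
| After Group 2, 20 Groups (21 runs) | 2/20 | 1.414/0.1 = 14.1 sigma |
| Last run, 10 or 20 Groups | 1 | 1.41 sigma |

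For the mean drift over subjects with the end repeat, 1.414/√10 = 0.45 sigma and 1.414/√20 = 0.32 sigma. These count reading error only; true variation in drift between subjects would add to them. Repeating Group 1 after every five Groups gains little per subject: 1.41 sigma (10 Groups, 12 runs) or 1.25 sigma (20 Groups, 24 runs).

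**4. Effect on the high-minus-low contrast.** With half the Groups of each type:
- One type entirely first: bias = (5/9)D = 0.56D for 10 Groups, (10/19)D = 0.53D for 20.
- Types alternating: bias = (1/9)D = 0.11D, or (1/19)D = 0.05D.

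| Assumed D (mA) | One type first (mA) | Alternating (mA) |
|---|---|---|
| 0.2 | 0.11 | 0.01–0.02 |
| 0.5 | 0.26–0.28 | 0.03–0.06 |
| 1.0 | 0.53–0.56 | 0.05–0.11 |
| 2.0 | 1.05–1.11 | 0.11–0.22 |

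If one type came first, an assumed drift of 0.5 mA would produce a spurious difference larger than the 0.2 mA step. The documents do not state the order of the density types.

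**The case against.** The strongest reply is that this is a pilot. Section D, item ii disclaims statistically valid results, item v calls the statistical analysis exploratory, and a repeat is already foreseen. That lowers the weight of the point but does not answer it. The same section promises a direct comparison of the two densities, and the issue is whether an observed difference can be interpreted, not power.

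Several stronger readings are tempting, and the documents do not support them.
- *Drift and Group effects can never be separated.* This holds only for the required measurements in one fixed order. A voluntary late repeat, or an order that varies between subjects, would help. Step 4-a does not say that the numbering is the same in every subject, and the neurosurgeon selects the patterns. If drift is linear and the order known, the pooled high-versus-low contrast is estimable, with variance inflation of about 4 if blocked and about 1 if alternating. The plan guarantees none of these conditions and plans no such model.
- *Every Group runs at one fixed amplitude, which drift would push further below threshold.* Step 4-a gives no value or percentage. The Figure 4 caption and item v both suggest that amplitudes vary between Groups.
- *Repeats would be made only after surprising responses.* Step 4-a names Group 1 and gives no such trigger.
- *A bi-pole reference in one subject and a tri-pole in another biases the result.* A difference in reference between subjects does not by itself bias a within-subject contrast.
- *Drift is known to occur.* The documents give no evidence of its presence or size.

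Appendices A and C are not in the supplied text. A repeat rule there would answer the point, although Step 4-a describes them as the case report form and exemplar contact patterns.

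**Conclusion.** The point holds as a low-cost improvement, not as a flaw that invalidates the study. Item v leans on a repeat rule that Step 4-a leaves undefined and optional, so the central comparison has no guaranteed measure of within-session change. Even a team that takes up the option where the sentence stands learns almost nothing about the full session.

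The aliasing rests on each Group being run once in a fixed order. The standard errors assume linear drift, equal spacing and independent reading errors. The mA figures also assume a drift size and a blocked order, and show scale only. The conclusion does not depend on whether 10 or 20 subjects are enrolled, nor on how amplitude is set for each Group.

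**What to change.** - **Step 4-a:** replace the permissive sentence on Group 1 with a requirement. In every subject, re-activate Group 1 at its original settings as the last stimulation before the Study Electrode is removed, within the existing time limit.
- **Step 4-a:** where possible, alternate high-resolution and low-density Groups instead of running one type first, and record the order actually used.
- **Section D, item v:** refer to this rule. Report the start-to-end change in the Group 1 EMG response, mainly pooled across subjects because one repeat is imprecise for a single subject, and read high- versus low-density differences against it.

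A repeat at unchanged settings shows change in the EMG response, not directly a threshold shift in mA. That is enough for this purpose, and a second threshold search is not needed.

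The cost is protocol wording, a place to record the repeat and the order, and about one Group slot: 1 to 2 minutes, displacing one exploratory Group. Section B heads the study as 20 minutes but lists 3 minutes for placement and 20 for Step 4, which should be reconciled. If placement counts, 17 minutes remain, or 17/20 = 0.85 to 17/10 = 1.7 minutes per Group, and the repeat still takes one slot.

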2. The proposed clinical study is summarized in Figure 3 with the left column describing the clinical standard of care procedure the patient will undergo and the right column indicating the additional Non-Significant Risk steps which the enrolled subjects would also undergo (additions shown in blue).

[figure not shown]

Figure 3. The standard of care procedure flow (left) is compared with the proposed study protocol (right).

Study Electrode (Micro-Leads, Inc., Boston, MA)

The high-resolution Study Electrode (Figure 2, middle) will be used to answer clinical research and scientific questions associated with performing high-resolution spinal cord stimulation. The Study Electrode will feature an array of 8 columns of stimulation contacts arranged in 8 rows with a low-volume electrode body. This array of stimulation electrodes contact patterns of bi-poles and tri-poles (Supplemental Materials, Appendix C) may be applied to the spinal cord for assessment of dermatomal selective stimulation patterns.

The Study Electrode will be manufactured specifically for this pilot study and will not be marketed or sold as a commercial product. The Study Electrode will be manufactured, tested for biocompatibility, sterilized with Ethylene Oxide, and provided in a sterile, double-pouch packaging with safety labelling according to 21 CFR 812.5. The Study Electrode will have multiple lead tails, at least three feet in length with non-implantable proximal connectors. The Study Electrode connectors will be physically

large (2 cm x 4 cm) to facilitate ease of intraoperative handling and to uniquely constrain the use of the lead to the intraoperative session.

Study Pulse Generator System

The focus of this study is to evaluate clinical feasibility of only the Study Electrode (but not the fully-implanted system), and to connect the Study Electrode to a clinically safe external pulse generator through a switch matrix.[22] The pulse width and frequency will be varied per standard of care. Pulse amplitude will be varied in 0.2 mA steps from 0 to 10 mA which are the same parameters used for clinical standard-of-care.

[figure not shown]

Figure 4. The Study Electrode will be connected to an external pulse generator using a sterile cable. The stimulation amplitudes will be changed along with different electrode contacts.

Detailed Intraoperative Description

Step 1. Surgical access to the epidural space (Standard Procedure, +0 minutes)

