The Permanent Electrode tails (wires) are tunneled beneath the skin to the location of the battery implant. The tails are connected to the header of the battery, and the device itself is tested for good conduction of the lead contacts. Once this is confirmed, small torque screws are tightened using a dedicated screwdriver. The IPG is placed and secured within the tissue pocket.

All surgical incisions are closed using a multi-layered suture technique for optimum wound healing. Dermabond is utilized on the incision after closure to provide a further integrity to the skin and create an antimicrobial barrier during epithelialization.

c. SUBJECT POPULATION (WHO, WHAT, WHERE)

- i. The subjects will be AMC neurosurgery patients with chronic pain who are undergoing or have undergone a neuromodulatory procedure (SCS).

- ii. Subject population will include 20 adults \geq 18 years old.
- iii. Patients participating in this study must also be fluent in English as well as mentally competent to read and answer the questionnaires, as well as complete pain assessments exams.
- iv. All patients must be able to give informed consent.

D. DATA ANALYSIS

- i. De-identified data will be provided to [name] at Micro-Leads, Inc. for the following analyses.
- ii. Statistically valid results are not the intent of investigational pilot studies, though the studies should still be performed with a purpose, enroll appropriate subjects, use meaningful endpoints, and capture relevant information to inform further device development.

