There is a possible risk that the contacts could break due to the size and fragility of the device. However, proper safety and friction testing including: a surgical simulation test, simulated tissue spine model test, and destructive mechanical insertion tests (frictional handling and insertion into a low-volume, narrow cavity) have been conducted by the manufacturer to ensure that this is a minimal risk. This will be explained to the patient. Minor risks of the proposed study include loss of confidentiality and increase in OR time by 20 minutes, which is within the normal variation of OR cases. Patients' names will only be associated with the data that is collected on a master list that will be kept on a password protected computer. A small risk of loss of confidentiality is present. Patients will be returned to the stimulation parameters most efficacious at controlling pain at the end of testing. Though thresholds are monitored carefully, there is a risk of discomfort.

F. BENEFITS

While we cannot promise any benefits to the patients in this study, there is the possibility of personal benefits to the participants of the study if a better lead becomes available in the future. Additionally, data obtained from this study may improve our knowledge of the effects of stimulation to aid future SCS patients in improved device programming.

G. CONFIDENTIALITY

PHI will include patients' name and date of birth. All data including the subject's name, electrophysiological data, video recordings obtained in clinic, and demographics will be kept on a password protected computer in a locked office in the AMC hospital. Each subject will be given a unique number and the collected data will be stored under that number. The master list linking patients' to their coded data will be password protected and only key study personnel will have access

to the master list. The master list of data will be stored indefinitely following the completion of the study.

[figure not shown]
H. OPTIONS

Patients have the right to opt out of the research study with no change in their normal standard of care.

I. REFERENCES

1. Gee, L., et al., *Spinal Cord Stimulation for the Treatment of Chronic Pain Reduces Opioid Use and Results in Superior Clinical Outcomes When Used Without Opioids*. Neurosurgery, 2018.

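### No masking of EMG reading or analysis to electrode configuration is described, and the manufacturer does the analysis, so the high- versus low-density comparison is open to observer bias

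*Combined protocol and SAP*

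**What the plan says.** - **Recording.** Section B, Step 4-a: "A designated team member will record the EMG results (see case report form, Appendix A"). The same step builds the paresthesia maps from the regions where neuromonitoring reports EMG activation. A low-density configuration groups two or more electrodes as one contact; a high-resolution configuration uses one. The neurosurgeon selects the patterns, and the numbered Groups run one after another.
- **Analysis.** Section D, item i: "De-identified data will be provided to [name] at Micro-Leads, Inc. for the following analyses". Section B names that company as the electrode's maker: "Study Electrode (Micro-Leads, Inc., Boston, MA"). The analyses listed in section D include the dermatome mapping (iii), the density comparison (iii and v) and the heat-map (vi).
- **Comparison.** Section D, item v: "The study is designed to perform a relative comparison between high-resolution and low-density Electrode Groups using the Study Electrode". Item iii asks whether high resolution improves targeting. The hypothesis in item iv has a different comparator: a response "focused to a more selective (smaller) dermatomal region than the currently available paddle electrodes according to the paresthesia maps".
- **Storage.** Section G: "electrophysiological data, video recordings obtained in clinic, and demographics will be kept on a password protected computer".
- **Not described in the supplied text.** Masking to configuration, coded Group labels, random order, independent reading, or a numerical criterion for EMG activation.

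**The concern.** Removing patient identity does not hide electrode configuration. An EMG trace is recorded by machine, but assigning a region as active is, on the supplied text, a call with no stated rule. After the threshold has been found with a central pole, the Groups are stimulated below it, so weak or borderline responses are plausible. The investigators frame the density question in one direction, and the analyst is the maker of the device.

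If borderline responses were discounted slightly more often in high-resolution Groups, those Groups would look more selective with no physiological difference behind it. Such a shift goes straight into the count of active regions, which is what selectivity means here, and enrolling more subjects does not shrink it. The plan intends the results to inform further device development, so a spurious selectivity signal would have consequences even in a pilot.

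**Working it through.** **Reading the text.** The plan states no alpha, power, effect size or variance, so it has no figure to reproduce. Side by side, the passages give this:

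| Question | What the text gives |
|---|---|
| Who records? | A designated team member (Step 4-a) |
| Does the recorder see the density? | Not stated; Groups are numbered, and Appendices A and C were not supplied |
| What counts as active? | What neuromonitoring reports; no numerical rule |
| Who analyses? | The manufacturer (section D, item i) |
| Is the analyst masked to configuration? | Not stated; only patient identity is removed |
| Is EMG stored per Group and channel? | Not stated; section G says only that electrophysiological data are kept |

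**Illustration of size.** Every input below is an assumption except the sample size. The protocol gives 10 subjects (section A) and 20 (sections B and C), so both are used.

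- No true mean difference; 3 active regions per Group; 5 high/low pairs per subject; SD of a pair difference 1; between-subject SD of the difference 0.3 or 1.
- A fraction u of active regions goes uncounted in high-resolution Groups only. Spurious shift = 3 × u, which is 0.15, 0.30 and 0.45 regions for u = 5%, 10% and 15%.
- SE = √[(1²/5 + SD²)/n]. With SD 0.3: √(0.29/10) = 0.170 and √(0.29/20) = 0.120. With SD 1: √(1.2/10) = 0.346 and √(1.2/20) = 0.245.
- Chance of falsely favouring high resolution = upper-tail rejection of a two-sided 5% paired t test, from the noncentral t with n − 1 degrees of freedom and noncentrality shift/SE. With u = 0 it is 2.5%.

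| Between-subject SD | Under-count u | Shift | n = 10 | n = 20 |
|---|---|---|---|---|
| 0.3 | 5% | 0.15 | 12% | 22% |
| 0.3 | 10% | 0.30 | 35% | 66% |
| 0.3 | 15% | 0.45 | 65% | 94% |
| 1 | 5% | 0.15 | 6% | 8% |
| 1 | 10% | 0.30 | 12% | 21% |
| 1 | 15% | 0.45 | 21% | 41% |

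**Second illustration, fewer assumptions.** Take one high-versus-low verdict per subject and an exact two-sided 5% sign test, which needs 9 of 10 or 15 of 20. With no bias, the chance of a false result for high resolution is 1.1% (n = 10) and 2.1% (n = 20). If unmasked reading moves the chance of a favourable verdict from 0.50 to 0.60, it is 4.6% and 12.6%; at 0.70 it is 14.9% and 41.6%. The direction is the same. In both illustrations the larger sample makes a false result more likely, because the shift stays while the noise falls.

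**The case against.** The strongest reply is that much of the case rests on silence. The recorder's form (Appendix A) and the pattern list (Appendix C) are not in the supplied text; either could hide the density or define activation. The study also says that statistically valid results are not its intent, so false-rejection rates describe a decision rule it does not have. Both points stand, and they limit the strength of the conclusion. They do not remove it. The same item of section D asks for meaningful endpoints, and item v says statistical analysis of the Groups will be explored.

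A second reply is that the manufacturer receives data after surgery and does not make the calls in theatre. The timing is right, and recording and analysis are separate routes for bias. But the work assigned to the manufacturer includes the mapping and the heat-map, so it is not remote from the outcome.

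A third is that "We do not believe that the Permanent Electrode will be able to achieve these outcomes" concerns the Permanent Electrode and not the density contrast. That is correct, and the sentence should not be used to show an expectation about density. Item iii supplies that expectation separately.

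A reader might also infer more than the text supports:

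- That the density label is visible to the recorder. No passage says so.
- That bias is present. Only the opening for it can be shown.
- That coding would remove it. The neurosurgeon still chooses patterns knowing the configuration, Groups run in sequence with no stated random order, and amplitude, itself compared between densities, could reveal the code unless withheld.
- That coding needs no added effort. Staffing is not described, and whoever holds the key cannot be the scorer.

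**Conclusion.** The point holds in limited form. The supplied text describes no masking to configuration at reading or analysis and no activation criterion, and the analyst is the manufacturer. The high- versus low-density comparison is therefore open to observer bias, with a plausible direction towards high resolution.

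The size is unknown. Across the assumed ranges (under-counting of 5% to 15%, between-subject SD of 0.3 to 1), the false-favourable rate runs from about 6% to 65% with 10 subjects and from 8% to 94% with 20. So wide a range shows sensitivity to small scoring differences; it does not estimate what will happen, and the pilot plans no such test. The point is worth acting on because coded scoring is a better method than the one described and is cheap, not because bias has been demonstrated.

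**What to change.** 1. Predefine the EMG criterion for calling a region active.
2. Before transfer to the manufacturer, have existing site staff who do not score replace Group number, contact map and stimulation amplitude with a random code per subject, and hold the key.
3. Apply the criterion to the stored EMG for each coded Group and lock the dermatome maps.
4. Release the key and the amplitudes, then run the high- versus low-density and amplitude comparisons.
5. Keep the theatre case report form as the source log, and report any disagreement between it and the coded scoring.
6. State in the protocol who sees the configuration at each stage, and confirm that EMG is stored per Group and channel. If it is not, code at least the recorded EMG results before analysis; that protects the analysis but not the reading.

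**Cost.** A coding step, a key-holder separate from the scorer, some rescoring and a short delay. Nothing changes in theatre.

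**Limits.** This reduces reading and analysis bias only. It does not deal with pattern selection by the neurosurgeon, the sequential order of Groups, or the comparison with the Permanent Electrode, which is tested after the Study Electrode has been removed.
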